5.1 Description

Each kit of DEXYCU contains a single dose for a single patient. The 2 mL glass vial is filled with 0.5 mL of 9% dexamethasone.

5.2 Treatment/Dosing Regimen

DEXYCU (dexamethasone intraocular suspension) 9%, administered as a single dose, intraocularly in the posterior chamber at the end of surgery. The dose is .005 mL of dexamethasone 9% (equivalent to 517 micrograms)

5.3 Method for Assigning Subjects to Treatment/Dosing Groups

Patients undergoing bilateral cataract surgery will be randomized to the DEXYCU group (standard postoperative cataract regimen + intraoperative DEXYCU) in one eye or the STANDARD group (standard postoperative cataract regimen). Randomization will be done after screening visit, prior to surgery on the first eye and will be done by coin flip. Patients who are randomly assigned to the DEXYCU group will receive a sequentially numbered drug kit.

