4.3 Subject Recruitment and Screening

Subjects will be recruited for the study from principal investigator's clinical practice. As part of the informed consent process, patients will be offered a DEXYCU injection and given a brochure/handout discussing DEXYCU. As part of the standard cataract evaluation process, both tear film osmolarity and corneal staining will be performed.

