4.4 Early Withdrawal of Subjects

Subjects will be carefully monitored after surgery, including visual acuity measurements, intraocular pressure measurements, anterior and posterior segment evaluation, as well as dry eye testing. If patients have an intraocular pressure elevation over 35mm that requires additional medication, they will be withdrawn from the study. Also, if patients require a deviation from the standard cataract postoperative regimen, they will be withdrawn from the study.

5 Investigational Product

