7.3 Subject Population(s) for Analysis

All patient who met inclusion criteria and complete the study will be included in the selection of subjects to be included in the analyses.

8 Safety and Adverse Events

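### Assignment is made before first-eye surgery although the groups differ only by an injection at its end, and the 4.3 offer of DEXYCU makes loss or switching in between more likely

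*Combined protocol and SAP*

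**What the plan says.** - **When assignment happens.** Sections 3.1, 5.3 and 8.4 carry the same rule: "Randomization will be done after screening visit, prior to surgery on the first eye and will be done by coin flip". The interval between flip and operation is not given.
- **What is assigned.** Patients are "randomized to the DEXYCU group (standard postoperative cataract regimen + intraoperative DEXYCU) in one eye or the STANDARD group". Both groups use the same postoperative drops (3.1), so the injection is the only stated difference.
- **When the injection is given.** Section 5.2: "administered as a single dose, intraocularly in the posterior chamber at the end of surgery".
- **What patients are told.** Section 4.3: "As part of the informed consent process, patients will be offered a DEXYCU injection and given a brochure/handout discussing DEXYCU".
- **Who is analysed.** Section 7.3: "All patient who met inclusion criteria and complete the study will be included in the selection of subjects to be included in the analyses".
- **Who is withdrawn.** Section 4.4 names two triggers: a pressure rise ("If patients have an intraocular pressure elevation over 35mm that requires additional medication, they will be withdrawn from the study") and a need to depart from the standard drops. Section 5.4 leaves continuation after a significant drop deviation to the investigator.

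No section describes concealment of the assignment or masking of the surgeon. None says how to handle a patient who is assigned but not injected, or who receives DEXYCU against assignment.

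**The concern.** Nothing written in the protocol needs the assignment to be known before the injection step. Making it earlier places at least one whole operation, and possibly days or weeks, between assignment and treatment. Two things can go wrong in that interval.

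First, the surgeon can operate knowing the group. Surgical handling could plausibly affect the ocular surface, which is where both primary endpoints (tear osmolarity and corneal staining) are measured.

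Second, patients can leave or change treatment for reasons tied to the group. On a between-patient reading, only those assigned to standard care are refused something they were offered at consent, and only those assigned to DEXYCU can have an injection withheld. Such losses would not be random, and the completers-only rule in 7.3 would remove from the analysis anyone who then did not finish. The offer could also colour the secondary endpoint, satisfaction with surgery.

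**Working it through.** **Step 1: order of events in the first eye.** Screening and consent, with the offer of DEXYCU (4.3); coin flip (5.3); operation; injection or none (5.2); common drops (3.1); visits at days 1, 7 and 21 (section 6). A flip just before the operation would comply with 5.3, so the time before surgery may be short. The operation itself always lies between flip and injection.

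**Step 2: what a later assignment would change.**

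| Source of loss or influence | Removed by assigning at the injection step? |
|---|---|
| Surgeon knows the group during first-eye surgery | Yes |
| Refusal, postponement or switching before the first-eye injection | Yes |
| Patient found unsuitable for injection during first-eye surgery | Yes, if left out before assignment |
| Second-eye assignment known before its surgery, if the fellow eye is the control | No |
| Withdrawals and exclusions after surgery (4.4, 5.4) | No |
| Completers-only analysis (7.3) | No, needs its own change |

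**Step 3: scale, under assumptions.** The 40 patients in 7.1 are a feasibility figure with no alpha, power, effect size, SD or dropout, so there is no calculation to reproduce. Assume a between-patient design, 20 per group, two-sided alpha 0.05, normal approximation and outcomes in SD units.

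- Difference detectable with 80% power: d = (1.960 + 0.842) × √(2/20) = 2.802 × 0.3162 = 0.886 SD.
- Let q be the share of the DEXYCU group lost or untreated between flip and injection.
- Kept as assigned, with untreated patients responding like controls: power = Φ[(1 − q)d / √(2/20) − 1.960]. At q = 10%: 0.797 / 0.3162 − 1.960 = 0.561, so power is 71.3%.
- Dropped: SE = √[1/20 + 1/(20(1 − q))] and power = Φ[d/SE − 1.960]. At q = 10%: SE = √(1/20 + 1/18) = 0.325, so power is 77.8%.
- Bias if dropped = q × Δ, where Δ is the SD difference between lost and retained patients. With s = bias/SE, the type I error is Φ(−1.960 + s) + Φ(−1.960 − s).

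| q | Patients of 20 | Power, kept | Power, dropped | Bias at Δ = 0.5 / 1 SD | Type I error at Δ = 1 SD |
|---|---|---|---|---|---|
| 0 | 0 | 80.0% | 80.0% | 0 / 0 | 5.0% |
| 5% | 1 | 75.9% | 79.0% | 0.025 / 0.05 SD | 5.3% |
| 10% | 2 | 71.3% | 77.8% | 0.05 / 0.10 SD | 6.1% |
| 20% | 4 | 61.1% | 75.2% | 0.10 / 0.20 SD | 9.2% |

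In terms of the whole trial, 5% to 10% of 40 is 2 to 4 patients. If all fell in one group of 20, that group would lose 2/20 = 10% to 4/20 = 20%. This is a worst case, because losses spread over both groups would partly offset in the bias. None of these rates comes from the documents.

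**The case against.** Assigning before surgery is a workable choice in a 40-patient pilot, and several stronger readings that a reader might infer are not supported.

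- **That the protocol excludes complicated cases after assignment.** It has no surgical exclusion. Section 4.2 has one preoperative criterion, and a withheld injection meets neither trigger in 4.4. Such a patient could complete and stay in the 7.3 set.
- **That patients know their group before surgery.** No section says so, and refusal or a request to switch would require it. The consent form was not available for this review, so 4.3 cannot be taken as all that patients are told about chance assignment.
- **That a later flip closes the gap altogether.** It does so for the first eye only. The words "in one eye" in 5.3 leave open a design with the fellow eye as control. One flip would then also settle the second eye, whose group is known until its own surgery. On that reading every patient is due DEXYCU in one eye, so the argument about denied patients weakens as well.
- **That there is no record of use.** Kits are numbered (5.3), use is logged (5.6), eye and surgery date are collected (9.1) and reasons for early exit are recorded (8.5). What is missing is a rule for treatment against assignment.

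There is also a risk in the remedy: a coin flipped once the surgical course is known could be repeated or skipped. Immediate recording reduces that risk but does not make a coin toss concealed or verifiable.

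These limits narrow the point. They leave standing that the early flip serves no stated purpose, that the surgeon can know the group while operating, and that the 4.3 wording does not fit random assignment.

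**Conclusion.** The point holds for the interval between assignment and injection in the first eye. The ordering in 3.1, 5.3 and 8.4 lets the group be known during the operation and lets patients be lost or switch before treatment, and 4.3 adds a reason for them to do so. This is an avoidable weakness that should be corrected; it is not shown to have biased anything.

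Its size is unknown, because the documents give neither the length of the interval nor any rate of refusal, switching or withheld injection. The tabulated power and bias figures illustrate scale on a between-patient reading with 20 per group and all losses in the DEXYCU group. Post-injection losses under 4.4 and 5.4, and second-eye knowledge on a within-patient reading, remain whatever the flip time.

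**What to change.** 1. **Sections 3.1, 5.3 and 8.4:** make the assignment at the end of first-eye surgery, immediately before the point of injection. Record it at once with the time and, for DEXYCU, the kit number. Patients whom the surgeon judges unsuitable for injection are then left out before assignment, which does not bias the comparison; list them as consented but not assigned.
2. **Section 4.3:** replace the offer of an injection with an offer to take part in a study where DEXYCU use is decided by chance.
3. **Section 7.3:** analyse every assigned patient with outcome data in the group assigned, including any treated against assignment. Without this, keeping patients in their group conflicts with the completers-only rule.
4. State in the same sections that this protects the first-eye interval only, and say whether the fellow eye is the control.

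The cost is wording in five sections (3.1, 4.3, 5.3, 7.3, 8.4) and an unopened kit on hand at each first surgery. Someone in the operating room must also make and record the assignment; the protocol does not say who does this now. No extra patients or visits are needed.

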1.1 Background

Multiple studies have established the relationship between dry eye and cataract surgery. First, a majority of patients undergoing cataract surgery have dry eye signs including decreased tear break up time (63%) and positive corneal staining (77%). Second, patients experience an increase in dry eye symptoms after cataract surgery compared to baseline. Third, Snellen visual acuity and contrast sensitivity are impacted by dry eye after cataract surgery.

The objective of this clinical research is to evaluate whether the signs and symptoms of dry eye after cataract surgery improve with the addition of a DEXYCU intraocular injection.

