7.1 Sample Size Determination

The determination of sample size was based on a review of similar cataract and dry eye studies. As this is a single center, pilot study, it was determined that a sample size of 40 patients would be feasible.

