7.2 Statistical Methods

An ANOVA analysis will be performed to compare the dry eye testing data between the DEXYCU group and the standard regimen group.

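### An unrestricted, unconcealed coin flip for 40 patients leaves group size (or, if the flip picks the eye, surgical-order balance) to chance; a concealed balanced list is a cheap, modest improvement

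*Combined protocol and SAP*

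**What the plan says.** Sections 3.1, 5.3 and 8.4 give the same allocation method: "Randomization will be done after screening visit, prior to surgery on the first eye and will be done by coin flip". None gives an allocation ratio, block, stratum, pre-generated list or means of concealment. The numbered kits in 5.3 go only to patients already assigned to DEXYCU, so they serve as neither a list nor concealment.

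The same sections say patients are "randomized to the DEXYCU group (standard postoperative cataract regimen + intraoperative DEXYCU) in one eye or the STANDARD group". This can be read as assigning the patient to a group, or as choosing which eye of each patient receives DEXYCU.

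On size, section 7.1 says "it was determined that a sample size of 40 patients would be feasible". It gives no effect, SD, alpha or power. On analysis, section 7.2 says "An ANOVA analysis will be performed to compare the dry eye testing data between the DEXYCU group and the standard regimen group", and names no term for surgical order, patient or baseline. Section 7.3 limits the analysis to completers: "All patient who met inclusion criteria and complete the study will be included".

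**The concern.** A coin puts no limit on how uneven 40 assignments can become, and nothing later in the plan corrects an uneven draw. The consequence depends on the unit of randomisation, and the two consequences are alternatives:

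- **Patient as unit.** The two groups may differ in size, which costs precision.
- **Eye as unit.** Every patient gives one eye to each arm, so arm sizes are equal. The number of DEXYCU eyes operated first rather than second is then uncontrolled, and part of any first-eye versus second-eye difference enters the one estimate the trial produces.

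On either reading a coin flip leaves no pre-existing record against which an assignment can be checked. Section 4.3 recruits from the principal investigator's own practice, section 10 has the principal investigator monitor the study, and no masking is described. A concealed list would protect against selective assignment. The documents do not describe one.

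**Working it through.** There is no sample-size calculation to reproduce, because 40 is a feasibility figure.

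**Inputs.** N = 40 patients (7.1). One fair flip per patient is inferred from 5.3. Two-sided alpha of 0.05, the effect sizes, the order effect and the dropout rates are assumptions, because the documents give none.

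**Group sizes, patient as unit.** For a split a:b, the tail probability comes from Binomial(40, 0.5), and effective N = 4ab/40. Power is from a two-sample t test with 38 degrees of freedom and noncentrality 0.909 × √(ab/40). The effect of 0.909 SD is chosen because it gives 80% power at 20:20.

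| Split | Chance of this or worse | Effective N | Noncentrality | Power |
|---|---|---|---|---|
| 20:20 | – | 40.0 | 2.87 | 80.0% |
| 25:15 | 15.4% | 4×25×15/40 = 37.5 | 2.78 | 77.4% |
| 26:14 | 8.1% | 4×26×14/40 = 36.4 | 2.74 | 76.2% |
| 27:13 | 3.8% | 4×27×13/40 = 35.1 | 2.69 | 74.7% |

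Exactly 20:20 occurs in 12.5% of trials. Write d = (a − b)/40. Its mean square is 1/40, so average effective N = 40 × (1 − 1/40) = 39.0. Power averaged over all draws is 78.9%, about 1 point below 80%. The result depends little on the assumed effect. By the normal approximation, effects giving 50% or 90% power at 20:20 average 49.0% and 89.2% under the coin, and give 45.1% and 85.9% at 27:13.

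**Surgical order, eye as unit.** Without an order term, the expected DEXYCU-minus-standard difference, given the draw, is the treatment effect plus d × (order effect), where d = (DEXYCU-first − DEXYCU-second)/40.

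- d averages zero over draws, and its mean absolute value is 0.125.
- At 25:15, d = 10/40 = 0.25.
- For assumed order effects of 0.1, 0.25, 0.5 and 1.0 SD of the within-patient difference, the shift at 25:15 is 0.025, 0.063, 0.125 and 0.25 SD. The standard error is 1/√40 = 0.158 SD.
- In 100,000 simulated paired t tests with no treatment effect and a 0.5 SD order effect, type I error was 5.0% over all draws and 10.5% among 26:14 draws. At 0.25 SD it was 4.9% and 6.3%.

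**After the fix.** At 20:20, d = 0. Order should still be in the model: with a 0.5 SD order effect, the unadjusted paired test at 20:20 has a type I error of 2.8%, so it is needlessly conservative. With completers only, and dropout unrelated to arm, exact balance survives with probability 51%, 40% and 31% at 5%, 10% and 20% dropout. The average efficiency loss over that range is 0.1% to 0.6%, against 2.6% to 3.1% for the coin.

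**The case against.** The strongest reply is that the coin does little harm. It costs one patient's worth of information on average. A fair flip is unpredictable beforehand and gives an unbiased estimate with about 5% type I error over all draws. An order term in the ANOVA would remove the order contribution without replacing the coin. All of this stands, and it is why the point is a modest one. What remains is that the trial is run once, that 7.2 names no order term, and that no concealment or checkable record is described.

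A reader might infer more than the documents support:

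- **That precision is lost and order also leaks.** These belong to mutually exclusive readings of 5.3. If the eye is the unit, arm sizes cannot differ by chance of the flip.
- **That the coin biases the DEXYCU effect.** The order contribution averages zero over draws, and the documents give no order effect to scale it.
- **That the coin causes imbalance in baseline staining.** With the 77% staining-positive rate from section 1.1, two groups of exactly 20 differ by at least 20 percentage points in 18.6% of trials. That describes an unstratified 20:20 list. Over coin-flip group sizes the figure is 14.5%. The 77% is also a background figure, and section 4.2 excludes central staining.
- **That a 20:20 list guarantees balance at analysis.** Section 4.4 says that "if patients require a deviation from the standard cataract postoperative regimen, they will be withdrawn from the study", and 7.3 then drops non-completers.

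**Conclusion.** The point holds as a recommended improvement, not a fault that invalidates the trial. The allocation method is unrestricted, no concealment is described, and nothing in the analysis compensates for an uneven draw. The size depends on the unit of randomisation, which the protocol must settle first. With the patient as unit, the cost is small on average and noticeable only in an unlucky draw. With the eye as unit, a quarter of any order effect enters the estimate at 25:15, and whether that matters depends on an unstated quantity. The figures assume one fair flip per patient and, for power, two-sided 0.05. The gain in precision from a list is modest. The main gains are an assignment that is concealed and can be audited, and protection against a badly unbalanced draw.

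**What to change.** 1. State in 3.1, 5.3 and 8.4 whether the flip assigns the patient or selects the eye.
2. Replace the coin with a computer-generated list, prepared by someone who does not enrol patients and held in sequentially numbered, opaque, sealed envelopes. With the patient as unit, balance it 20:20 on arm. With the eye as unit, balance it at 20 DEXYCU-first and 20 DEXYCU-second.
3. In 7.2, if the eye is the unit, include patient and surgical order in the model. On either reading, adjust for baseline staining and osmolarity, which are already measured at screening. Do this in place of stratifying: a single permutation of 40 cannot also be stratified, and separate lists with unknown stratum sizes would not guarantee 20:20.

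The cost is about an hour to generate the list and fill 40 envelopes. There are two drawbacks. With no masking described, the last assignments can be guessed by anyone who knows the earlier ones; using one large block and hiding the list from the person enrolling keeps this small. Withdrawals may also undo exact balance.

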5.4 Subject Compliance Monitoring

The study team will assess and track compliance on each study visit (1 day, 1 week, 3 weeks). At all postoperative visits, the study team will monitor adherence to the eyedrop regimen. If there is a significant deviation from the eyedrop regimen, the principal investigator will determine continuation in the study.

A case report binder will be created for each subject in the study. Binder tabs will include:

- Screening Visit
- Day 1 Visit
- Day 7 Visit
- Day 21 Visit
- Exit Form
- Early Exit Visit
- Nonserious Adverse Event Forms
- Serious Adverse Event Forms

5.5 Prior and Concomitant Therapy

All medications that subjects are taking prior to cataract surgery will be permitted. Subjects are also permitted to utilize artificial tears in addition to the therapeutic regimens. The use of artificial tears will be tracked by the study team.

5.6 Packaging, Receiving, Storage, Dispensing and Return

Dexycu will be stored in a locked cabinet. Usage of the medication will be logged.

6 Study Procedures

- Screening Visit
- Day 1 Postoperative Visit
- Day 7 Postoperative Visit
- Day 21 Postoperative Visit

At all visits, visual acuity, eye pressure measurements, tear film osmolarity, and corneal staining will be measured and recorded. At days 7 and 21, patient satisfaction scores will be measured.

7 Statistical Procedures

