1.6 Risk/Benefits

The following adverse events rates are derived from three clinical trials in which 339 patients received the 517 microgram dose of DEXYCU. The most commonly reported adverse reactions occurred in 5-15% of subjects and included increases in intraocular pressure, corneal edema, and iritis. Other ocular adverse reactions occurring in 1-5% of subjects included, corneal endothelial cell loss, blepharitis, eye pain, cystoid macular edema, dry eye, ocular inflammation, posterior capsular opacification, blurred vision, reduced visual acuity, vitreous floaters, foreign body sensation, photophobia, and vitreous detachment.

2 Study Objectives

The objective of this clinical research is to evaluate whether the signs and symptoms of dry eye after cataract surgery improve with the addition of a DEXYCU intraocular injection. Multiple studies have established that dry eye worsens after cataract surgery. There is also

a strong body of evidence that shows that dry eye is inflammatory. The objective of this study is to evaluate whether the intraocular use of steroid impacts dry eye.

3 Study Design

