3.2 Primary/Secondary Endpoints

Primary endpoints:

- 1) Tear film Osmolarity as measured on Tear Lab system
- 2) Corneal Staining (Oxford grading scale 0-15)

Secondary endpoint:

- 3) Satisfaction questionnaire – How satisfied are you with your surgery? (Graded 0-4)

4 Subject Selection and Withdrawal

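### IOP, visual acuity and adverse events have no planned by-group safety summary, and the completers-only set drops patients withdrawn for high IOP

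*Combined protocol and SAP*

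**What the plan says.** - **Known harms (1.6).** "The most commonly reported adverse reactions occurred in 5-15% of subjects and included increases in intraocular pressure, corneal edema, and iritis". The source is 339 patients given the 517 microgram dose in three trials.
- **Endpoints (3.2).** Tear film osmolarity and corneal staining are primary; a satisfaction score is secondary. No safety outcome is named.
- **Monitoring and withdrawal (4.4).** Patients are followed after surgery, "including visual acuity measurements, intraocular pressure measurements, anterior and posterior segment evaluation, as well as dry eye testing". Then: "If patients have an intraocular pressure elevation over 35mm that requires additional medication, they will be withdrawn from the study". A patient who needs to depart from the standard postoperative regimen is also withdrawn.
- **Recorded data (section 6 and 9.1).** "At all visits, visual acuity, eye pressure measurements, tear film osmolarity, and corneal staining will be measured and recorded". The 9.1 list also has IOP and acuity, with three graded symptoms.
- **Analysis (7.2).** "An ANOVA analysis will be performed to compare the dry eye testing data between the DEXYCU group and the standard regimen group".
- **Analysis set (7.3).** Patients who met the inclusion criteria and completed the study.
- **Adverse events (8.1).** An event is defined by its occurrence in a patient who received DEXYCU. A form is mandatory for every nonserious event, whether or not it is thought related.

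**The concern.** DEXYCU is added to a full course of topical steroid, and the protocol itself lists the reactions to expect. IOP bears directly on the first of them and is measured in everyone at every visit, but its only stated use is as a withdrawal trigger. Followed to the letter, the plan could produce a report of dry eye benefit with no account by group of IOP, acuity or adverse events, and a reader could not set the benefit against the harms in 1.6.

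This is more than a missing table. If someone later summarised IOP in the only population that 7.3 defines, the patients with the most marked rises would already have been removed, and the summary would look safer than what happened.

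**Working it through.** The plan gives no safety figure to reproduce. Its sample size of 40 (7.1) rests on feasibility. The check is therefore mainly of the text, with arithmetic for scale.

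**1. Is IOP or acuity summarised by group anywhere?** Both are recorded (section 6, 9.1). Neither is in 3.2, and 7.2 is confined to dry eye testing. The answer is no.

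**2. Who is left in the analysis set?** IOP over 35 mm requiring medication leads to withdrawal (4.4). A withdrawn patient does not complete, so is not in the 7.3 set. The same holds for any reaction that requires a departure from the standard regimen.

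**3. Can adverse events be counted by group?** This depends on the randomised unit, which 3.1 and 5.3 leave unclear.
- If patients are randomised to DEXYCU or STANDARD, the 8.1 definition does not reach STANDARD patients, so there is no control count.
- If each patient has one DEXYCU eye and one control eye, every patient falls under the definition, but no summary by eye is planned.

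**4. Scale.** Inputs: 40 patients (7.1) and 5-15% (1.6). Assumptions: patients are the unit, the coin flip gives about 20 per group, and 5-15% applies to each of the three reactions within 21 days.
- Expected cases of each reaction: 20 × 0.05 = 1 to 20 × 0.15 = 3.
- Chance of at least one case, 1 − (1 − p)^20: 0.64 at 5%, 0.88 at 10%, 0.96 at 15%.
- Upper limit with 0 of 20: one-sided 95%, 1 − 0.05^(1/20) = 13.9%; two-sided 95%, 1 − 0.025^(1/20) = 16.8%.

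**5. What losing one case does.** Suppose one of 20 DEXYCU patients is withdrawn for IOP.
- All treated patients: 1/20 = 5%. The one-sided 95% upper limit solves (1 − p)^20 + 20p(1 − p)^19 = 0.05, giving p = 21.6%.
- Completers only: 0/19, with upper limit 1 − 0.05^(1/19) = 14.6%.

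The documents do not say how many IOP rises would meet the 4.4 criterion. Under the assumptions in step 4, the expected number in the DEXYCU group lies between 0 and the 1-3 expected for any IOP rise.

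**6. Would a formal comparison help?** For illustrative rates of 15% and 5%, 20 per group and two-sided 0.05, power is 18% by normal approximation and 7% by Fisher's exact test; 80% power needs 141 per group. Description is the realistic aim.

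**The case against.** The strongest reply is that this is a 40-patient, single-center pilot of an approved product with a dry eye objective. It cannot test safety, and 8.1 already makes adverse event forms mandatory. The first part stands: step 6 confirms it, so no test or larger sample is asked for. The forms are a real route of capture, but no analysis uses them, and under patient-level randomisation the definition leaves out the control group.

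A reader might go further and infer that corneal edema and iritis are examined for but never recorded, because section 6 and 9.1 have no segment finding. The documents do not support this:
- 4.4 names segment evaluation in general terms, not those two conditions.
- 9.2 says that copies of the source forms are included. They are not in the text available here and may hold a segment field.
- The 9.1 list describes data for confidentiality purposes. It omits adverse events, which 8.1 requires to be reported, so it is not exhaustive.
- Either condition would qualify for a mandatory form under 8.1.

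Two other extensions also fail. Scaling to 2-6 cases in 40 DEXYCU eyes applies a per-subject rate to eyes. Calling the investigator unmasked is an inference, because the protocol does not say who is masked. The safety-assessment heading that appears on the contents page but not in the body adds little, since the numbering and headings differ elsewhere too (8.4, 9.4).

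Finally, 1.6 gives neither an observation window nor a comparator rate, so the scale in step 4 is indicative only.

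**Conclusion.** The point holds for the analysis plan. No safety outcome is named, and IOP and acuity are collected at every visit without a by-group summary. Sections 4.4 and 7.3 together exclude the patients with the IOP rises that matter most. The adverse event gap is conditional: if patients are the randomised unit, the 8.1 definition prevents a by-group count.

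The claim that corneal edema and iritis go unrecorded is not established and is left as a conditional item in the fix.

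Under the stated assumptions, 1-3 cases of each reaction are expected among about 20 DEXYCU patients. Zero observed would still be compatible with a rate of about 14% (one-sided 95%), so one case lost from the set alters what can be said. The change should be made. It affects the safety account and leaves the dry eye comparison as it is.

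**What to change.** - **3.2 and 7.2:** name as descriptive safety outcomes IOP (change from screening, and the number meeting the 4.4 withdrawal criterion exactly as written, including the need for medication), visual acuity and adverse events.
- **7.3:** add a safety set of all operated study patients or eyes in both groups, using readings up to and at withdrawal.
- **8.1:** apply the adverse event definition to both groups.
- **Reporting:** tabulate by group and visit, with counts and confidence intervals at the level of the randomised unit, or with allowance for two eyes per patient. Exact intervals that treat eyes as independent would not do if both eyes of a patient contribute. No formal test.
- **Conditional:** if the source forms do not already hold the result of the segment evaluation required by 4.4, add it to section 6 and 9.1.

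The cost is one descriptive table and possibly a few form fields. No clinical rule changes; the 4.4 criterion is used only for reporting.
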